7.8 ABNORMAL LABORATORY VALUES

Laboratory abnormalities are usually not r corded as AEs or ' AEs. However, laboratory abnormalities (e.g., serum chemistry, CBC, CPK, urinalysis) independent of the underlying medical condition that require medical or surgical intervention or lead to IP interruption or discontinuation must be recorded as an AE, as well as an SAE, if applicable. In addition, laboratory or other abnormal assessments (e.g., electrocardiogram, x-rays, vital signs) that are associated with signs and/or symptoms must be recorded as an AE or SAE if they meet the definition of an AE (or SAE) as described in Section 7.1. If the laboratory result (e.g., decreased hemoglobin).

Any laboratory abnormality that is new in onset or worsened in severity or frequency from the baseline condition and meets one of the following criteria will be recorded as an AE:

- Requires therapeutic intervention or diagnostic tests
- Leads to discontinuation of study treatment
- Has accompanying or inducing symptoms or signs
- Is judged by the investigator as clinically significant

Severity will be assessed as detailed in Section 7.6.

7.9 POST-STUDY REPORTING REQUIREMENTS

All AEs and SAEs including deaths, regardless of cause or relationship, must be reported for subjects on study (including any protocol-required post-treatment follow-up).

Investigators are not obligated to actively seek AEs or SAEs beyond the follow up period for subjects. However, if the investigator learns of an AE or SAE that occurs after the completion or termination visit

Version Date: 01Jun2022

CONFIDENTIAL

Version 4.1

Page 67 of 87

and the event is deemed by the investigator to be related to the study treatment, he/she should promptly document and report the event to the Sponsor.

7.10 EVENT REPORTING FOR DISEASE PROGRESSION OR EXCLUSIONARY HISTOLOGIC FINDINGS POST-STUDY TREATMENT

After starting study treatment, if there is histologic confirmation of progression of cervical HSIL to micro invasive or invasive squamous cell carcinoma, the event must be reported as an SAE. Post-study treatment histologic diagnosis of adenocarcinoma-in-situ or adenocarcinoma should also be reported as an SAE. In both instances, the condition for SAE reporting should be categorized as a medically important event unless another criterion is met.

7.11 PROCEDURE FOR REPORTING PREGNANCY DURING THE STUDY

Subjects who are pregnant or expect to become pregnant prior to Week 36 of the study will be excluded from participation in the study. Should a subject become pregnant fer randomization, she will not be given any further treatments with the investigational product. . Pregnancy Form will be completed by the investigator and submitted to the sponsor study team and nedica. nit r within 24 hours after learning of the pregnancy. Site personnel will submit the Pregnancy Form to the Sponsor or its designee by fax, as described in Section 7.15.3. The investigator will also report this event o the IRB/EC within 24 hours of becoming aware of the pregnancy. Sites must requise the subject's per ission to query pregnancy outcome and follow each subject to determine the outcome of the pregnan y. Results will be summarized in the Clinical Study Report (CSR).

Subjects who become pregnant at any point during the study will continue to be followed for safety assessments without receiving further IP. Procedures that are contraindicated during pregnancy, including additional treatments, must not be performed. Invest, ators should use clinical judgment regarding subsequent study-related blood collection based on the presence or absence of anemia in each subject. Subjects who are not withdrawn will continue to be followed for safety assessments to study discharge per protocol.

All pregnancies that occu from the time of first study treatment through the follow up visits must be reported. The investigator will monitor the subject and follow the outcome of the pregnancy. If the end of the pregnancy occurs after the study has b en completed, the outcome will be reported directly to the study team and the Medical Monitor.

METHODS AND TIMING OF COLLECTION OF SAFETY DATA 7.12

Non-serious AEs and SAEs (and UADEs) will be collected for each subject from the time when informed consent is obtained through Week 40.

The sources of AEs cover:

- The subject's response to questions about her health (a standard non-leading question such as 'How have you been feeling since your last visit?' is asked at each visit).
- Symptoms spontaneously reported by the subject.
- Evaluations and examinations where the findings are assessed by the investigator to be clinically significant changes or abnormalities.

Version Date: 01Jun2022

CONFIDENTIAL

Version 4.1

Page 68 of 87

• Other information relating to the subject's health becoming known to the investigator (e.g., hospitalization).

All AEs will be reported on the appropriate CRF. Any SAE (or UADE) occurring during the course of the study must be reported to the Sponsor within 24 hours of awareness.

7.13 SAFETY AND TOXICITY MANAGEMENT

The Medical Monitor will be responsible for the overall safety monitoring of the study.

Safety assessments include the following:

- Incidence of all adverse events classified by system organ class (SOC), preferred term, severity, and relationship to study treatment
- Local and systemic injection site review; special atten n will be paid to the examination of the injection site. Administration site reactions and the s bject's complaints will be documented

7.14 ADVERSE EVENTS OF SPECIAL INTEREST

Adverse Events of special interest (AESI) are the adverse events d em⁷ d related to VGX-3100/Placebo delivered with the CELLECTRATM device that require expedited c⁷ munication from the site to the Sponsor and meet any of the following criteria:

- Grade 3 or greater persistent administration site erythema, and/or induration recorded ≥ 2 hours immediately after Study Treatment
- Grade 4 or greater persistent administration site pain, tenderness recorded ≥ 2 hours immediately after Study Treatment
- Grade 3 or greater fever
- Grade 3 or greater systemic symptoms (e.g., malaise, chills, fatigue), including generalized pruritus

Sites will inform the Sponsor via the method described in Section 7.15.2 within 24 hours to discuss whether further dosing for the particulation of the section of the sect

7.15 ADVERSE EXPERIENCE (AE) REPORTING

To assure the safety of the participants, information about all AEs (see Section 7.2), whether volunteered by the subject, discovered by investigator or study staff questioning, or detected through physical examination, laboratory test or other means, will be collected and recorded in the subject's source documents and followed as appropriate.

7.15.1 STUDY REPORTING PERIOD OF ADVERSE EVENTS

All solicited and unsolicited adverse events will be collected throughout the study and recorded in the EDC system. The Study Report will analyze and summarize all adverse events throughout the study. Emphasis will be placed on the following:

- Certain AEs of interest will be solicited during the 7 days following each administration of Study Treatment and summarized separately
- Unsolicited AEs will be collected and summarized for the entire study period

Version Date: 01Jun2022

CONFIDENTIAL

Version 4.1

Page 69 of 87

Downloaded by

7.15.2 STUDY REPORTING PERIOD FOR ADVERSE EVENTS OF SPECIAL INTEREST

Adverse events of special interest (AESI) (see Section 7.14) require expedited communication from the site to the Sponsor. Within 24 hours of the site's awareness of the event, AESI must be reported by the investigator through data entry in the Adverse Event electronic case report form (eCRF) via the Medidata RAVE electronic data capture (EDC) system. In the event that the Medidata RAVE EDC system is unavailable, the investigator must notify the Sponsor via email or phone.

AESI reporting if EDC system is unavailable

EMAIL:				
SAFETY PHONE:				

7.15.3 STUDY REPORTING PERIOD OF SURIO, SADVERSE EVENTS

The reporting period for SAEs (without regard to caus .ity or relationship) is comprised of the period following the signing of the informed consent form unt the end of the study.

Each AE will be assessed to determine whether it meets seriousness criteria. If the AE is considered serious, the investigator should report this event to the Sponsor within 24 hours of becoming aware of the event. The investigator may also directly report this event to the IRB/r C according to its standard operating procedures. Expectedness of SAEs will be determined by the S^o onsor using reference safety information specified in the Investigator's Brochure. An event may qualify for expedited reporting to regulatory authorities if it is an SAE, unexpected per reference safety information and considered related following the guidelines in Section 7.4 (Suspected Unexpected Serious Adverse Reaction, SUSAR) and 7.5 (Unanticipated [Serious] Adverse evice Effect) in line with relevant legislation. All investigators will receive a safety letter notifying t .m of all SUSAR reports. The investigator should notify the IRB/EC as soon as is practical, of serious events in writing w^{j} ere this is required by local regulatory authorities, and in accordance with the local institutional policy.

Within 24 hours of the site's awareness of the event, all SAEs (regardless of relationship to investigational product) must be reported by the investigator through data entry in the Adverse Event electronic case report form (eCRF) via the Medidata RAVE electronic data capture (EDC) system. In the event that the Medidata RAVE EDC system is unavailable, the paper SAE Report form should be used and faxed to the PPD Pharmacovigilance (PVG) Safety Hotline Fax Number shown below:

Facsimile (FAX) reporting if required^a:

Americas FAX#:					
Europe FAX#:					
3D (1 EAV: 110	CAED	(F	·C 1 /	· 1 /	

^a Reporting by FAX is required for paper SAE Report Forms if electronic data capture (EDC) is not available, redacted supporting medical records, and Pregnancy Report Forms.

All supporting documents for SAE reports, including medical records and diagnostic test results, will include reference to the study subject number. The study site will redact all other patient identifying

Version Date: 01Jun2022

CONFIDENTIAL

Version 4.1

Page 70 of 87
information present on SAE supporting documents prior to sending the report to the Sponsor. The supporting documents for SAE reports should be sent by fax to the PPD PVG Safety Hotline Fax Number, shown above.

Investigator will supply the Sponsor and the IRB/EC with more information as it becomes available and any additional requested information. The Sponsor or its representative will be responsible for determining and in turn, reporting SAEs to regulatory authorities according to the applicable regulatory requirements.

SAEs must be followed by the investigator until resolution, even if this extends beyond the study-reporting period. Resolution of an SAE is defined as the return to baseline status or stabilization of the condition with the expectation that it will remain chronic.

In the event of death, if an autopsy is performed, a copy of the report will be sent to the Sponsor.

7.16 NOTIFICATIONS OF SERIOUS ADVERSE EVENTS

In accordance with local regulations, the Sponsor shall notify the appropriate regulatory authorities and all participating investigators in a written safety report of any adverse drug reaction that is both serious and unexpected and any significant new safety informati a that might mate ially influence the benefit-risk assessment of a medicinal product, sufficient to consider changes in product administration or overall conduct of a clinical investigation. The Sponsor will notify regulat ry agencies within the time frame specified by local requirements but no later than 10 working days for UADE, 7 days for a fatal or life-threatening SUSAR, and 15 days for a 1 other SUSARs see Section 7.5 and 7.4). Results of investigations of other safety information s all be submitted, as appropriate, in an information amendment or annual report.

7.17 REPORTING OF DEVICE RELATED COMPLAINTS OR DEFICIENCIES

A product complaint/device deficiency is defined as any written, electronic, or oral communication that alleges deficiencies or inadequacies of the device or components related to the identity, quality, durability, reliability, safety, effectiveness, or performance of the device or components after it is released for distribution within the clinical investigation. All product complaints that meet this definition (with the exception of SAEs requiring 24 hr reporting) must be reported to the Sponsor with 10 days of discovery.

Device deficiencies include malfunctions, use errors and inadequate labeling. A malfunction is defined as the failure of a device to meet its performance specifications or otherwise perform as intended. The intended performance of a device refers to the intended use for which the device is labeled or marketed.

Any problems experienced during the treatment procedure including potential malfunctions of the device, error messages displayed on the device screen following treatment or errors that occur during the treatment procedure must be reported to the Sponsor or designee immediately for evaluation.

The error reporting form must be completed and emailed to the Sponsor at: or fax to

7.18 STUDY DISCONTINUATION

Inovio Pharmaceuticals reserves the right to discontinue the study at this site or at multiple sites for safety or administrative reasons at any time. In particular, a site that does not recruit at a reasonable rate may be discontinued. Should the study be terminated and/or the site closed for whatever reason, all non-source

Version Date: 01Jun2022

CONFIDENTIAL

Version 4.1

Page 71 of 87

Downloaded by

documentation and study product pertaining to the study must be returned to Inovio Pharmaceuticals or its representative.

The study may be discontinued at any time by an IRB/EC, Inovio Pharmaceuticals Inc., the FDA or other government agencies as part of their duties to ensure that research subjects are protected.

8 STATISTICAL CONSIDERATIONS

8.1 STATISTICAL AND ANALYTICAL PLAN

The formal Statistical Analysis Plan is contained in the sections that follow.

8.2 GENERAL CONSIDERATIONS

The statistical analysis of the data will be performed by Inovio Pharmaceuticals or its representative.

This is a two-arm, multi-center, placebo-controlled, blinded a' drandomized clinical trial in subjects with a histologic diagnosis of cervical HSIL. The study's primary endpoint is binary: regression to CIN1/normal and clearance of HPV-16 and/or HPV-18 infection, based on tissue collected at the Week 36 timeframe. The primary hypothesis is that VGX-3100 will be superior to placebo regarding the proportion who achieve the primary endpoint among baseline biomarker-positive women. Sc condary efficacy analyses involve regression to CIN1 and complete regression, cle .ance of HPV-16 and/or HPV-18 infection from cervical and non-cervical tissue, and non-progression of cervical lesions. Other secondary analyses concern safety, humoral and cellular immunological measures.

8.3 STATISTICAL HYPOTHESES

The true treatment effect on the primary endpoint is $\delta = p_V - p_P$, where p_V and p_P denote the true biomarkerpositive population probabilities of the primary endpoint for VGX-3100 and Placebo, respectively. The primary hypothesis of superiority is: H_0 : $\delta \le 0$ vs. H_1 : $\delta > 0$. There are no other formal hypotheses.

8.4 ANALYSIS POPULATIONS/DATASETS

Analysis populations will include:

The intention to treat (ITT) population includes all subjects who are randomized. Subjects in this sample will be grouped to treatment arms as randomized. Analysis of the ITT biomarker-positive population will be primary for the analysis of efficacy in this study.

The modified intention to treat (mITT) population includes all subjects who receive at least one dose of Study Treatment and who have the analysis endpoint of interest. Subjects in this sample will be grouped to treatment arms as randomized. Analysis of the mITT population will be considered supportive for the corresponding ITT population for the analysis of efficacy.

The per-protocol (PP) population comprises subjects who receive all doses of Study Treatments and have no protocol violations and who have the analysis endpoint of interest. Subjects in this sample will be grouped to treatment arms as randomized. Analyses on the PP population will be considered supportive of

Version Date: 01Jun2022

CONFIDENTIAL

Version 4.1

Page 72 of 87

the corresponding ITT population for the analysis of efficacy. Subjects excluded from the PP population will be identified and documented prior to unblinding of the study database.

The safety analysis set includes all subjects who receive at least one does of Study Treatment. Subjects will be analyzed as to the treatment received.

8.5 DESCRIPTION OF STATISTICAL METHODS

8.5.1 ANALYSIS OF THE PRIMARY EFFICACY ENDPOINT

The true treatment effect on the primary endpoint is $\delta = p_V - p_P$, where p_V and p_P denote the true biomarkerpositive population probabilities of the primary endpoint for VGX-3100 and Placebo, respectively. The primary hypothesis of superiority is:

H₀:
$$\delta \leq 0$$
 vs. H₁: $\delta > 0$.

A p-value for this hypothesis test and corresponding 95% confidence interval will be computed based on the method of Miettinen and Nurminen [17]. Superiority will be concluded if the one-sided p-value is <0.025 and the corresponding lower bound of the two-sided 95% CI exceeds zero.

The efficacy time frame is defined by those who have undergone a biopsy or surgical excision at any time starting from 14 days prior to the protocol-specified target date of Week 36. It also includes subjects who undergo early excision or biopsy on or after ose 1 but prior to this time frame or subjects who have no endpoint data for this time frame; these subjects are consid red as failures for the primary efficacy endpoints. Table 4 provides details for the definition of the primary endpoint response.

The ITT biomarker-positive populatio. will be primary f r the analysis of efficacy in this study. Missing data will be considered as non-regr ssors (failures) for the ITT efficacy analysis. Efficacy analysis using the mITT population will also be conducted and will serve as sensitivity analyses regarding missing data. The PP population will also be used for a supportive analysis. An additional analysis on the PP population will utilize the Week 36 timeframe su. .ega dless of excision or biopsy performed before the Week 36 time frame, thus serving as a sensitivity analysis regarding early intervention. Additional analyses will be performed on all subjects reg $\sqrt{s} \sqrt{t'}$ varker status.

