8.7 RANDOMIZATION AND BLINDING

Subjects will be randomized (2 VGX-3100:1 Placebo) in a stratified manner according to a) the degree of CIN observed in the biopsy specimens at screening (C $\sqrt{2}$ vs. CIN3), b) BMI category (≤ 25 vs. ≥ 25 kg/m²) on Day 0, and c) age category (≤ 25 years vs. ≥ 25 years) on Day 0. There will be no pre-determined number of subjects required to be randomized within each stratum. To ensure that milder CIN2 disease is not overrepresented in the study, the percentage of subjects enrolled with CIN2 will not exceed 50% of the total enrolled. A group of sequential allocation nu bers will be design ted for use by each participating country.

The study is double blinded. Randomization and blinding will avoid bias in the assignment of participants to treatment, increase the likelihood that known and unkn wn subject attributes (e.g., demographics and other baseline characteristics) are evenly balanced betw en treatment groups, and enable valid statistical comparisons between treatment groups.

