9.5.6 CHANGES TO THE PROTOCOL

The investigator should not implement any deviation from or changes to the protocol without approval by Sponsor and prior review and documented approval/favorable opinion from the IRB/EC of a protocol amendment, except where necessary to eliminate immediate hazards to study subjects, or when the changes involve only logistical or administrative aspects of the study (e.g., change in monitors, change of telephone numbers). While every effort should be made to avoid protocol deviations, should a deviation be discovered, Sponsor must be informed immediately. Any prot 👞 eviation impacting subject safety must be reported to the Medical Monitor immediately.

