4.2. Randomization, Stratification, and Blinding

Subjects will be randomized (2 VGX-3100:1 Placebo) in a stratified manner according to a) the degree of CIN observed in the biopsy specimens at screening (CIN2 vs. CIN3), b) Body Mass Index (BMI) category (≤ 25 vs. ≥ 25 kg/m²) on Day 0 visit, and c) age category (≤ 25 years vs. ≥ 25 years) on Day 0 visit. There will be no pre-determined number of subjects required to be randomized within each stratum. To ensure that milder CIN2 disease is not over-represented in the study, the percentage of subjects enrolled with CIN2 will not exceed 50% of the total enrolled. Each country will receive a group of sequential allocation numbers.

The study is double-blinded to both investigators and subjects.

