Age (years), height (cm), weight (kg), BMI (kg/m²), and years of education (years) will be summarized as continuous variables. BMI (in kg/m²) is defined as the subject's weight (in kg) divided by the square of their height (in m). The number and percentage of subjects will be presented for categorical variables including race, ethnicity, gender, stratification factors (CIN grade (CIN2 vs. CIN3), BMI (≤ 25 vs. ≥ 25), age (≤ 25 vs. ≥ 25)), and type(s) of healthcare insurance.

Summaries will be performed on the baseline biomarker-positive subjects and on all subjects (regardless of biomarker status) separately. Demographic listings will flag all subjects who are baseline biomarker positive.

A separate listing will be provided for stratification errors.

6.2.Reproductive History and Status

The number and percentage of subjects with reproductive potential and current use of contraception method will be summarized. For the subjects who are not of reproductive potential, the reason will be summarized.

For the subjects who have ever been pregnant, the age of first pregnancy, as well as pregnancy related information will be summarized based on the collection at screening.

6.3.Alcohol and Tobacco Usage

The number of subjects who consumed alcohol, number of alcoholic drinks per day, and number of drink days per week will be summarized.

Passive smoking will be summarized by number of subjects with history of exposure, living with a permanent householder who smokes daily, and number of hours/day of passive smoke.

Smoking will be summarized by the smoke type and duration of smoke. For the cigarette type, number of packs/day will also be summarized. Duration of smoke is calculated by (the stop year - start year + 1) when both years are available. If the stop year is ongoing, it will be set to the year of the study visit.

Substance usage will be summarized at Screening, Week 36, and Week 40. Number of subjects with change from baseline will also be summarized at each post-baseline visit.

6.4.Medical History

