8.1.1. Primary Efficacy Endpoint

The primary efficacy endpoint is the proportion of baseline biomarker-positive subjects with no evidence of cervical HSIL (i.e., no evidence of CIN2, CIN3) on histology sample and no evidence of HPV-16 and/or HPV-18 in cervical samples by type specific HPV testing at the Week 36 timeframe.

The primary hypothesis of superiority is:

H₀: $\delta \leq 0$ vs. H₁: $\delta > 0$,

where $\delta = Pv - Pp$, and Pv and Pp denote the true biomarker-positive population probabilities of the primary endpoint for VGX-3100 and Placebo, respectively. The proportion in each treatment arm is calculated by the number of responders divided by the total number of responders and non-responders in the study population of the corresponding treatment arm. The detailed definitions of responder and non-responder are listed in Table 1.

For the primary endpoint, week 36 histology is evaluated based on the first biopsy or surgical excision procedure on or after Day 238; in case of multiple results on the same day, the one with worst grade will be used. The virology results used for analysis must be the latest result that is on or before the same date as the histology result and is taken on or after Day 238. If

a subject undergoes excision or cervical biopsy at any time on or after Day 1 and before Day 238, the subject will be considered as non-responder. Number of responders and non-responders, proportion of responders in each treatment arm, and difference of proportions between the two treatment arms will be presented. A p-value of superiority based on a test of risk difference and corresponding 95% confidence interval using the method of Miettinen and Nurminen [5] will be computed. Superiority will be concluded if the one-sided p-value is <0.025 and the corresponding lower bound of the 95% CI exceeds zero.

Responder proportion will also be summarized based on the stratification factors separately.

Responder	Non-Responder

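### The primary Miettinen-Nurminen test ignores the randomisation strata in a biomarker-positive subset of about 44 vs 22, and the visible plan has no adjusted analysis for a chance CIN imbalance

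*Protocol*

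**What the plan says.** Protocol 8.7 and SAP 4.2 allocate 2:1 "in a stratified manner according to a) the degree of CIN observed in the biopsy specimens at screening", BMI category and age category. Biomarker status is not a stratification factor. Protocol 8.7 also caps CIN2 at half of enrolment, with the reason given as "To ensure that milder CIN2 disease is not overrepresented in the study".

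The primary analysis set is the biomarker-positive part of the ITT population (Protocol 8.4). On the test, Protocol 8.5.1 states: "A p-value for this hypothesis test and corresponding 95% confidence interval will be computed based on the method of Miettinen and Nurminen". SAP 8.1.1 repeats this as "A p-value of superiority based on a test of risk difference and corresponding 95% confidence interval using the method of Miettinen and Nurminen" and fixes the estimate as crude: "The proportion in each treatment arm is calculated by the number of responders divided by the total number of responders and non-responders". Neither document names strata, weights or covariates. The secondary efficacy endpoints use the same method without p-values (Protocol 8.5.2.1, SAP 8.1.2).

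Two displays bear on the strata. SAP 6.1 tabulates "categorical variables including race, ethnicity, gender, stratification factors (CIN grade (CIN2 vs. CIN3" and the other factors, separately for biomarker-positive women. SAP 8.1.1 adds: "Responder proportion will also be summarized based on the stratification factors separately". The supportive analyses that can be read (mITT, PP, and PP ignoring early tissue removal) change the population or the handling of early procedures; none adjusts for strata. The only efficacy subgroup analysis is by prophylactic vaccine history. The exploratory efficacy text is blacked out in both documents.

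**The concern.** The sponsor treats CIN grade as important enough to stratify on and to cap, and then leaves it out of the analysis. The test is restricted to a one-third subset that was not itself stratified, so much of the CIN balance achieved in all 198 women is lost.

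If CIN grade predicts response, a chance imbalance moves the trial's single hypothesis test up or down. The baseline table would reveal it, and the response rates by CIN grade would hint at its effect, but they supply no pooled adjusted difference, interval or p-value. Any adjustment chosen after unblinding would be post hoc, whichever way it pointed.

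**Working it through.** **Inputs from the documents.** 198 randomised 2:1; 33% biomarker-positive; response 66% vs 15% with missing data already counted as failures; stated power above 90% (Protocol 8.6, SAP 4.1); one-sided alpha 0.025 (Protocol 8.5.1); CIN2 at most 50% (Protocol 8.7).

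**Assumptions, because the documents are silent.** Permuted blocks of 6 within the 8 strata; biomarker status independent of CIN grade; CIN2 share 50% (the cap); and a CIN2-CIN3 response gap of 0, 10 or 20 points in both arms, or 20 on placebo with 30 on VGX-3100.

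**1. The plan's own figure.** Biomarker-positive women: 198 × 0.33 = 65.3, split 43.6 vs 21.8, about 44 vs 22. The pooled rate is (0.66 × 44 + 0.15 × 22)/66 = 0.49.
- Null SE = √[0.49 × 0.51 × (1/44 + 1/22)] = 0.1305.
- Alternative SE = √[0.66 × 0.34/44 + 0.15 × 0.85/22] = 0.1044.
- Power = Φ[(0.51 − 1.96 × 0.1305)/0.1044] = Φ(2.43) = 99.3%.

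Exact binomial power of the crude score test at 44 vs 22 is 98.8%. It averages 98.5% when the number of biomarker-positive women per arm varies at random. The stated power above 90% is met.

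**2. How large a CIN imbalance to expect.** With 44 and 22 women split freely and half CIN2, the SD of the between-arm difference in CIN2 share is √[0.25 × (1/44 + 1/22)] = 13 points. Stratifying all 198 helps in part: the subset is a 33% sample of balanced arms, so the variance is multiplied by about 0.67 and the SD becomes 13.1 × √0.67 = 10.7 points. Simulating the full design gives 11 points. The difference reaches 15 points or more in 17.6% of trials, about 8.8% in each direction (14% of trials in total if 70% are CIN3).

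**3. Effect on the estimate.** With the same gap in both arms, shift in the crude difference = imbalance × response gap. Among trials with an imbalance of at least 15 points the mean is about 20 points, so the shift is 20 × 0.10 = 2 points or 20 × 0.20 = 4 points. For the 20/30 gap it is 4.7 points. The stratified estimate moves by under 1 point. Over all trials the crude estimate is unbiased to within about 0.1 point.

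**4. Power, crude then stratified.** The crude statistic is z = (pV − pP)/√[p(1 − p)(1/nV + 1/nP)·N/(N − 1)], where p is the pooled rate. The stratified one sums the differences over the two CIN strata with Mantel-Haenszel weights nV·nP/n. There were 40,000 simulated trials per scenario.

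| True rates | Gap 0 | Gap 10 | Gap 20 | Gap 20/30 |
|---|---|---|---|---|
| 66% vs 15% | 98.4 → 98.3 | 98.4 → 98.5 | 98.6 → 98.9 | 98.6 → 99.1 |
| 50% vs 15% | 81.8 → 81.4 | 81.6 → 81.7 | 82.1 → 83.5 | 82.0 → 84.8 |
| 45% vs 15% | 69.6 → 69.1 | 69.8 → 69.8 | 69.6 → 71.3 | 69.7 → 73.1 |

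**5. One-sided type I error** (60,000 trials per scenario, null rates 15% and 30%). Over all trials it is 1.6-2.3% crude and 1.7-2.3% stratified. Among the roughly 9% of trials with at least 15 points more CIN2 on VGX-3100, crude error is 1.8-2.1% at gap 0, 2.6-3.4% at gap 10 and 3.9-4.1% at gap 20, against 1.4-2.4% stratified.

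A separate calculation at a null rate of 30% and a 20-point gap fixed the split at 27/44 vs 9/22 CIN2, a 20-point excess on VGX-3100. It gave 4.3% crude and 2.4% stratified. With the imbalance reversed (18/44 vs 13/22), crude error falls to 0.9%, which is why the overall rate stays below 2.5%.

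**The case against.** The strongest reply is that there is no error here, only a choice between two valid tests. The crude test controls type I error, is unbiased on average and has more power than stated. At the planned rates stratifying moves power by at most half a point. Even taking the largest conditional shift above, 4.7 points, off the planned 51-point effect leaves about 96% power. The larger gains need both a smaller effect than planned and a CIN gap of 20 points or more, and no passage gives any gap. The subset is also selected by a signature meant to predict response, so how much CIN grade still predicts within it is unknown. The raised conditional type I error belongs to one tail and is offset by the other. A 50% CIN2 share is the cap, which makes the imbalance close to its largest. Finally, an adjusted model could sit in the blacked-out exploratory text.

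All of that stands and limits the size of the point. It does not supply a pre-specified answer if an imbalance appears. The tables by CIN grade are descriptive, and the all-women analysis answers a different question. An exploratory model, if there is one, would not be the primary analysis.

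**Conclusion.** The concern holds as an improvement that should be made, not as a flaw that invalidates the test. The primary analysis uses crude proportions in about 44 vs 22 women and adjusts for none of the factors the trial randomises by, and no visible primary, secondary or supportive efficacy analysis does either. A CIN imbalance of 15 points or more would arise in about one trial in six. It would move the crude difference by about 2 to 5 points if the CIN response gap is 10 to 30 points, and not at all if CIN grade is not prognostic. The benefit is negligible at 66% vs 15%. It reaches about 3 points of power only if the effect is much smaller and the gap is large.

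Confidence is medium, because the size rests on the assumed CIN gap, block size, CIN2 share and independence of biomarker status from CIN grade.

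**What to change.** Before unblinding, amend Protocol 8.5.1 and SAP 8.1.1 so that the primary test and interval are Miettinen-Nurminen stratified by randomised CIN grade (two strata, Mantel-Haenszel weights), and keep the unstratified result as a sensitivity analysis. At minimum, leave the primary test as it is and name the CIN-stratified version as a pre-specified sensitivity analysis.

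Use CIN grade alone. It is the only stratum whose severity the documents comment on, and eight cells over about 65 women are too sparse: at 45% vs 15%, power is 69.0% with all eight against 69.8% unstratified.

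The cost is a SAP update, one programming option and a protocol amendment, which under Protocol 9.5.6 needs sponsor approval and "prior review and documented approval/favorable opinion from the IRB/EC of a protocol amendment". No new data or patients are needed. If CIN grade turns out not to be prognostic, stratifying costs about 0.1 point of power at the planned rates and about 0.5 point at 45% vs 15%.
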